1.2 SCHEMA

Figure 2 - Graphical study design - Cohort D1 and D2

C=Study cycle; D=Study day; EOT=end of treatment; IMP=Investigational medicinal product; Q9W= every 9 weeks; Q12W=every 12 weeks.

1.3 SCHEDULE OF ACTIVITIES (SOA)

Evaluation ^a	Screening	Treatment Period ^b						End of Treatment	Observation Period ^c			Survival Phone Call Follow-up ^d	Notes
		Cycle 1			Cycle 2 and beyond ^e				Follow-Up	Follow-Up	Follow-Up		
		Visit 1	Visit 2	Visit 3+	Phone Call FU								
Cycle Day (Visit window in Days)	D-28 to D-1	D1	D8 ^f (±1)	D15 ^f (±1)	D1 (±3)	D8 (±1)	D15 (±1)	30 days (+/-7 days) after last IMP or at initiation of further therapy	3 months after last IMP admin ±7 days	6 months after last IMP admin ±7 days	Every 3 months after FU Visit 2 ±7 days	Every 3 months +/-14 days	
Informed consent	X												
Inclusion and exclusion criteria	X												
IRT contact	X	X			X			X					
Demography, medical/surgical and disease history	X												See Section 8 of the master protocol
Body Weight/ Height ^g	X	X	X	X	X			X	X				
Full physical examination	X							X					See Section 8.2.1 of the master protocol
Directed Physical examination		X	X	X	X				X				See Section 8.2.1 of the master protocol

Evaluation ^a	Screening	Treatment Period ^b						End of Treatment	Observation Period ^c			Survival Phone Call Follow-up ^d	Notes	
		Cycle 1			Cycle 2 and beyond ^e			EOT Visit	Follow-Up	Follow-Up	Follow-Up	Phone Call FU		
		Visit 1	Visit 2	Visit 3+										
Cycle Day (Visit window in Days)	D-28 to D-1	D1	D8 ^f (±1)	D15 ^f (±1)	D1 (±3)	D8 (±1)	D15 (±1)	30 days (+/- 7 days) after last IMP or at initiation of further therapy	3 months after last IMP admin ±7 days	6 months after last IMP admin ±7 days	Every 3 months after FU Visit 2 ±7 days	Every 3 months +/-14 days		
Vital Signs	X	X	X	X	X			X	X				See Section 8.2.2 of the master protocol	
Performance status (ECOG)	X	X	X	X	X			X	X					
SpO ₂	X	As clinically indicated												
Laboratory and other investigations														
12-Lead ECG	X	X	As clinically indicated										See Section 8.2.3 of the master protocol	
LVEF	X	As clinically indicated											See Section 8.2.3 of the master protocol	
Troponin	X	As clinically indicated		X (Cycle 4 Day 1)		As clinically indicated							See Section 8.2.3 of the master protocol and Section 10.2 of the master protocol	

Evaluation ^a	Screening	Treatment Period ^b						End of Treatment	Observation Period ^c			Survival Phone Call Follow-up ^d	Notes	
		Cycle 1			Cycle 2 and beyond ^e		EOT Visit		Follow- Up	Follow-Up	Follow-Up			
		Visit 1	Visit 2	Visit 3+	Phone Call FU									
Cycle Day (Visit window in Days)	D-28 to D-1	D1	D8 ^f (±1)	D15 ^f (±1)	D1 (±3)	D8 (±1)	D15 (±1)	30 days (+/- 7 days) after last IMP or at initiation of further therapy	3 months after last IMP admin ±7 days	6 months after last IMP admin ±7 days	Every 3 months after FU Visit 2 ±7 days	Every 3 months +/-14 days		
Pregnancy test	X	X			X			X	X	X			See Section 8.2.5 of the master protocol and Section 10.2 of the master protocol	
Hepatitis serology, CD4 counts and viral load	X ^h	As clinically indicated											See Section 10.2 of the master protocol and Section 10.7 of the master protocol	
Hematology	X	X	X	X	X			X	X				See Section 10.2 of the master protocol	
Coagulation	X	As clinically indicated											See Section 10.2 of the master protocol	
Blood Chemistry	X	X	X	X	X			X	X				See Section 10.2 of the master protocol	

Evaluation ^a	Screening	Treatment Period ^b						End of Treatment	Observation Period ^c			Survival Phone Call Follow-up ^d	Notes	
		Cycle 1			Cycle 2 and beyond ^e			EOT Visit	Follow-Up	Follow-Up	Follow-Up	Phone Call FU		
		Visit 1	Visit 2	Visit 3+										
Cycle Day (Visit window in Days)	D-28 to D-1	D1	D8 ^f (±1)	D15 ^f (±1)	D1 (±3)	D8 (±1)	D15 (±1)	30 days (+/- 7 days) after last IMP or at initiation of further therapy	3 months after last IMP admin ±7 days	6 months after last IMP admin ±7 days	Every 3 months after FU Visit 2 ±7 days	Every 3 months +/-14 days		
Urinalysis ⁱ	X	X			X			X	X				See Section 10.2 of the master protocol	
T3, FT4, TSH & cortisol (Cohort D1 only) ^j	X				X			X	X				See Section 10.2	
Electrolytes (Cohort D2 only)		weekly under treatment and then at the end of treatment, at FU Visit 1 and as clinically indicated												
IMP														
SAR444245		X			X									
Pembrolizumab (Cohort D1 only)		X			X									
Cetuximab (Cohort D2 only)		X	X	X	X	X	X							
Hospitalization ^k		X												
AE/SAE assessment ^l	X	Continuously throughout treatment period						X					See Section 8.3 of the master protocol	
Prior/Concomitant Meds	X	Continuously throughout treatment period											See Section 6.8 of the master protocol	

[figure not shown]
Evaluation ^a	Screening	Treatment Period ^b						End of Treatment	Observation Period ^c			Survival Phone Call Follow-up ^d	Notes	
		Cycle 1			Cycle 2 and beyond ^e			EOT Visit	Follow-Up	Follow-Up	Follow-Up	Phone Call FU		
		Visit 1	Visit 2	Visit 3+										
Cycle Day (Visit window in Days)	D-28 to D-1	D1	D8 ^f (±1)	D15 ^f (±1)	D1 (±3)	D8 (±1)	D15 (±1)	30 days (+/- 7 days) after last IMP or at initiation of further therapy	3 months after last IMP admin ±7 days	6 months after last IMP admin ±7 days	Every 3 months after FU Visit 2 ±7 days	Every 3 months +/-14 days		
First subsequent anti-cancer therapy								X	X	X	X	X		
Survival status												X		
Pharmacokinetic (PK) / Pharmacodynamic (PDy) / Immunogenicity assessments														
PK SAR444245	See PK flowcharts in Section 1.5.1 and Section 1.5.2													
PK Cetuximab	See PK flowcharts in Section 1.5													
ADA SAR444245	See PK flowcharts in Section 1.5.1 and Section 1.5.2													
PDy - Blood and tumor tissue collection ^{m,n}	See Biomarker flowchart in Section 1.4													
Tumor assessment														
Brain imaging ^o	X												See Section 8.1 of the master protocol	
CT/MRI ^p	X				X			X	X	X	X		See Section 8.1 of the master protocol	

- a Evaluation: Screening assessments to be performed prior to first IMP administration unless otherwise indicated. There is no need to perform Cycle 1 Day 1 laboratory assessments that have been performed as part of screening within 3 days prior to first IMP administration. During the study treatment period, all assessments must be performed, and results should be reviewed by the investigator prior to IMP administration at that visit. After Cycle 1, samples for laboratory assessments (excluding PK & biomarker) can be collected up to 3 days prior to IMP administration. ICF must be signed before any study-specific procedures are performed and can be signed more than 28 days prior to first IMP administration. Screening time indicates the maximum time frame relative to the first IMP administration in which study procedures used to support eligibility are done.
- b Cycle: a treatment cycle is 21 days. See details in [Section 6.1](#) for IMP administration. If treatment cycles are adjusted, all procedures except tumor assessment imaging will be completed according to the cycle number. Tumor assessment imaging will be performed at fixed time points from C1D1 regardless of any treatment delays.
- c Observation Period: Participants who enter the Observation period will be followed differently depending on the reason leading to permanent IMP discontinuation. See [Section 4.1](#). For participant's convenience, all Follow-up assessments may occur during the same visit as that when tumor assessment is performed.
- d Survival Phone Call Follow-Up Period: Once the participant stops the tumor assessments due to PD or starts a new antineoplastic therapy, the participant moves into the Survival Follow-up Period and should be contacted by telephone approximately every 3 months \pm 14 days to assess for survival status. Updated survival status may be requested by the Sponsor at any time during the study.
- e For Cycle 4 visits, please refer to PK flowchart in [Section 1.5](#).
- f C1D8 and/or C1D15 visits must be performed on site for the following participants only: 1) Participants scheduled to have blood draws for biomarker assessment and/or ADA on Day 8; 2) Participants who will receive IMP on Day 8 and Day 15. For all other participants, these 2 on-site visits may be done remotely as appropriate based on investigator's discretion per institutional standard and local regulations. If this is the case, this must be documented in the source document. Sponsor may decide to cancel safety assessment on C1D8 and C1D15 if safety data justifies it.
- g Weight/Height: Height is required at baseline only. Weight is required at Screening and prior to starting each infusion. The total dose will be calculated based on the weight on the day of the infusion or the most recent weight assuming it was assessed in a reasonable time frame according to Investigator assessment. Study sites should make every effort to measure body weight as close to the infusion day as possible considering the variability of local process from site to site. If the infusion is prepared with the most recent weight assessed in a reasonable time frame, this will not prevent to assess the weight on D1 of each cycle.
- h For participants with known HIV, hepatitis B and hepatitis C infection under antiviral treatment to confirm controlled infection, and for all participants in Germany and Italy (see details and specific instructions in Section 10.2 and Section 10.7 of the master protocol).
- i Urinalysis using dipstick for glucose, blood, pH, protein, ketones, leukocytes and microscopic examination (if blood or protein is abnormal), will be performed every 4 cycles during Treatment Period and as clinically indicated.
- j Endocrine function tests will be performed every 2 cycles throughout the entire treatment period and at EOT. During the Observation Period, they will be performed at Follow-Up Visit 1. They can also be performed as clinically indicated.
- k Only for participants who will participate in the intensive PK sample collection.
- l AE/SAE assessment: Severity will be graded according to NCI-CTCAE v 5.0. ICANS and CRS will be graded using ASTCT criteria integrated with central laboratory cytokine results ([1](#)).
- m If a tumor biopsy was obtained from a target lesion during eligibility assessment, it is preferred to obtain a new baseline scan.
- n Will not be done for participants enrolled in China.
- o Brain imaging: For participants with no previous history of brain metastases, screening brain imaging will need to be obtained. MRI is the preferred imaging modality however CT is acceptable if an MRI is clinically contraindicated. Patients with asymptomatic brain metastases (ie, no neurological symptoms, no requirements for corticosteroids, and no lesion >1.5 cm) may participate but will require regular imaging of the brain as a site of disease as per protocol tumor assessment (TA) schedule. In all other cases, the lesions must be treated. Two additional scans, obtained at least 4 weeks apart, should be obtained to document disease stability after local treatment administration to the brain metastases has been completed. If participants receive therapy during these 4 weeks stabilization at the treating physician's discretion, it will be considered as part of prior anti-cancer therapy. Participants with previously treated brain metastases may participate provided they are stable, which is defined as lack of progression on two sets of imaging obtained at least 4 weeks apart. Stability as defined above should be documented prior to the first dose of trial treatment. In addition, any neurologic symptoms must have returned to baseline or have resolved, and the participant is not using steroids for at least 14 days prior to study treatment. The screening brain scan may be collected up to 42 days prior to enrollment.

p CT/MRI: The initial tumor imaging will be performed within 28 days prior to C1D1. Scans performed as part of routine clinical management are acceptable for use as the screening scan if they are of diagnostic quality and performed within 28 days prior to the date of enrollment. On study imaging will be performed every 9 weeks (63 ± 7 days) after the date of first IMP and if clinically indicated. Imaging studies should follow calendar days and should not be adjusted for delays in cycle starts or extension. The same imaging technique should be used in a participant throughout the trial. After week 45, tumor imaging should be performed every 12 weeks (84 ± 7 days). CT scan of the chest, abdomen, pelvis and any other locations with suspicion or evidence of disease involvement is required for the baseline assessment, during treatment period until PD. Per the primary tumor assessment criteria, after the first documentation of response or the first documentation of progression (if the participant is clinically stable), confirmatory imaging may be performed no fewer than 28 days later. Alternately, the scan performed at the next scheduled time point (eg, every 63 ± 7 days) may be used as confirmation. Tumor assessment is not needed for participants who start another anti-cancer therapy.

Abbreviations: ADA=anti-drug antibodies; AE=adverse event; AST=aspartate transaminase; ALT=alanine transaminase; C=Cycle; ANC=Absolute neutrophil count; AP=Alkaline phosphatase; BUN=Blood urea nitrogen; CRF=case report form; CRS=Cytokine release syndrome; CT=computed tomography; [REDACTED]; D=Day; ECG=electrocardiogram; ECOG=Eastern Cooperative Oncology Group; e-CRF=electronic case report form; EOT=end-of-treatment; FT4=free thyroxine; FU=follow-up; HBsAg=Hepatitis B surface antigen; HCV=Hepatitis C virus; ICF=Informed consent form; IMP=investigational medicinal product; INR=international normalized ratio; LDH=Lactate hydrogenase; LVEF=left ventricular ejection fraction; MRI=magnetic resonance imaging; MUGA= multigated acquisition; PD=progressive disease; [REDACTED]; PDy=pharmacodynamic; PK=pharmacokinetic; PR=partial response; PS=Performance Status; SpO2=oxygen saturation; Q3W=every 3 weeks; RECIST=Response Evaluation Criteria in Solid Tumors; SAE=serious adverse event; T3=tri-iodothyronine; TSH=thyroid stimulating hormone; WBC=White blood cells.

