Cetuximab can cause dermatologic toxicities, including acneiform rash, skin drying and fissuring, paronychial inflammation, infectious sequelae (for example, *S. aureus* sepsis, abscess formation, cellulitis, blepharitis, conjunctivitis, keratitis/ulcerative keratitis with decreased visual acuity, cheilitis), and hypertrichosis. Acneiform rash occurred in 82% of patients across clinical trials. Grades 3 or 4 acneiform rash occurred in 9.7% of patients. Acneiform rash usually developed within the first two weeks of therapy; the rash lasted more than 28 days after stopping treatment in

most patients. Life-threatening and fatal bullous mucocutaneous disease with blisters, erosions, and skin sloughing, has been observed. It could not be determined whether these mucocutaneous adverse reactions were directly related to EGFR inhibition or to idiosyncratic immune-related effects (eg, Stevens-Johnson syndrome or toxic epidermal necrolysis).

Cetuximab can cause hypomagnesemia which occurred in 55% patients in various clinical trials, including Grades 3 and 4 in 6% to 17%. Hypomagnesemia and accompanying electrolyte abnormalities can occur days to months after initiating treatment. It is recommended to monitor patients weekly during treatment for hypomagnesemia, hypocalcemia, and hypokalemia, and for at least 8 weeks following the completion of treatment and to replete electrolytes as necessary.

Based on animal data and its mechanism of action, cetuximab can cause fetal harm when administered to a pregnant woman. There are no available data for cetuximab exposure in pregnant women. In an animal reproduction study, intravenous administration of cetuximab once weekly to pregnant cynomolgus monkeys resulted in an increased incidence of embryo-lethality and abortion. Disruption or depletion of EGFR in animal models results in impairment of embryo-fetal development including effects on placental, lung, cardiac, skin, and neural development.

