5.2 EXCLUSION CRITERIA

Participants are excluded from the study if any of the following criteria apply (in addition to the criteria listed in the master protocol):

Medical conditions

E 01. Electrolyte (magnesium, calcium, potassium) levels outside of normal ranges for participants in Cohort D2.

Prior/concomitant therapy

E 02. *For participants in Cohort D1.* - Prior treatment with an agent (approved or investigational) that blocks the PD-1/PD-L1 pathway (participants who joined a study with an anti-PD-1/PD-L1 but have written confirmation they were on control arm are allowed).

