10.2 APPENDIX 2: CLINICAL LABORATORY TESTS

Clinical laboratory tests that are common to all cohorts are detailed in the master protocol. Cohort D1 and D2 specific evaluations are presented in [Table 14](#).

Table 14 - Protocol-required laboratory tests

Endocrine function tests ^a	Thyroid-stimulating hormone (TSH) Tri-iodothyronine (T3) Free thyroxine (FT4) Cortisol (preferably in the morning)
---------------------------------------	---

NOTES :

a Endocrine function tests will be performed every 2 cycles throughout the entire treatment period and at EOT in cohorts receiving pembrolizumab. During the Observation Period, they will be performed at Follow-Up Visit 1. They can also be performed as clinically indicated.

In addition, for participants in Cohort D2, electrolytes to be done weekly under treatment and then at the end of treatment, at FU visit 1 and as clinically indicated. After last IMP administration, additional electrolytes monitoring for Cohort D2, outside the visits, may be done according to the local standard institutional care.

10.3 APPENDIX 3: AES AND SAES: DEFINITIONS AND PROCEDURES FOR RECORDING, EVALUATING, FOLLOW-UP, AND REPORTING

Please refer to the master protocol.

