Hepatotoxicity	
Pembrolizumab
 
Hepatitis occurred in 0.8% of patients, including Grade 2, 3 or 4 cases in 0.1%, 0.5% and 0.1% patients, respectively, receiving pembrolizumab. The median time to onset of hepatitis was 3.6 months (range 8 days to 21.4 months). The median duration was 1.1 months (range 1 day to 20.9+ months). Hepatitis led to discontinuation of pembrolizumab in 0.3% patients. Hepatitis resolved in 36 patients.
 
Cetuximab
 
Increase in liver enzymes is very common
	
Exclusion of participants with impaired liver functions.
 
Monitor clinical signs and symptoms of hepatic impairment as part of TEAE. Monitor liver function parameters (AST, ALT, bilirubin & ALP) regularly from screening and throughout the study.
 
Dose modification and treatment guidelines for liver enzyme increase are provided under immune-related reactions in Table 9.

Nephrotoxicity	
Pembrolizumab
 
Common: nephritis, acute kidney injury
 
Cetuximab
 
Not reported in the SmPC
	
Dose modification and treatment guidelines for nephrotoxicity are provided under immune-related reactions in Table 9.

Hypomagnesaemia	
Cetuximab
 
Hypomagnesaemia is very common
	
Exclusion of participants with electrolytes (magnesium, calcium, potassium) outside the normal ranges.
 
Monitor electrolytes regularly as per protocol.

Neurological AEs	
Pembrolizumab
 
Dizziness, headache, neuropathy peripheral, dysgeusia (very common) and lethargy (common) for pembrolizumab in combination with chemotherapy
 
Uncommon: epilepsy.
 
Cetuximab:
 
Headaches are common
	
Dose modification and treatment guidelines for neurological AEs are provided under immune-related reactions in Table 9.

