Cardiovascular effects, including QT interval prolongation	
Cetuximab
 
Cardiopulmonary arrest or sudden death have occurred in 2-3% patients with squamous cell carcinoma of the head and neck receiving cetuximab with radiation therapy or a cetuximab product with platinum-based therapy and fluorouracil cetuximab. A history of coronary artery disease, congestive heart failure, or arrhythmias and abnormal serum electrolytes may be predisposing factors.
	
Specifically, for patients receiving cetuximab, exclude patients with electrolytes (magnesium, calcium and potassium) <LLN and monitor serum electrolytes weekly during and for at least 8 weeks after last cetuximab administration.

Immune-mediated Adverse Events	
Pembrolizumab
 
Immune-mediated adverse events are designated as important identified risk for pembrolizumab.
 
Cetuximab
 
Not reported as such in the SmPC.
	
Dose modification and treatment guidelines for immune-related reactions are provided in Table 9.
 
Patients treated with cetuximab:
 
If a diagnosis of ulcerative keratitis is confirmed, treatment with cetuximab should be

Potential risk of clinical significance	Summary of data/rationale for risk	Mitigation strategy
	
Patients presenting with signs and symptoms suggestive of keratitis such as acute or worsening: eye inflammation, lacrimation, light sensitivity, blurred vision, eye pain and/or red eye should be referred promptly to an ophthalmology specialist.
 
Very rarely, Stevens-Johnson syndrome/toxic epidermal necrolysis may occur in patients treated with cetuximab.
	
interrupted or discontinued. If keratitis is diagnosed, the benefits and risks of continuing treatment should be carefully considered. Cetuximab should be used with caution in patients with a history of keratitis, ulcerative keratitis or severe dry eye. Contact lens use is also a risk factor for keratitis and ulceration.

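### Cohort D2: the risk table states weekly electrolyte monitoring for at least 8 weeks after the last cetuximab dose, but the schedule fixes one test in that period

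*Protocol*

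**What the plan says.** All references are to substudy 04 of the protocol, Cohort D2 (SAR444245 plus cetuximab).

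**Monitoring after treatment**
- Section 1.3, electrolytes row (Cohort D2 only): "weekly under treatment and then at the end of treatment, at FU Visit 1 and as clinically indicated".
- Appendix 10.2 (clinical laboratory tests): the same time points. Additional monitoring after the last study drug, "outside the visits, may be done according to the local standard institutional care".
- Appendix 10.11, Table 15, cardiovascular row, mitigation column: "monitor serum electrolytes weekly during and for at least 8 weeks after last cetuximab administration".
- Section 2.3.1.2 (cetuximab risks): a recommendation of weekly monitoring during treatment "and for at least 8 weeks following the completion of treatment".
- Table 15, hypomagnesaemia row: regular monitoring as the protocol lays down, with no stated duration.

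**Exclusion threshold**
- Section 5.2, criterion E 01: "Electrolyte (magnesium, calcium, potassium) levels outside of normal ranges for participants in Cohort D2".
- Table 15, hypomagnesaemia row: "Exclusion of participants with electrolytes (magnesium, calcium, potassium) outside the normal ranges".
- Table 15, cardiovascular row: "exclude patients with electrolytes (magnesium, calcium and potassium) <LLN".

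**The concern.** The protocol treats electrolyte disturbance as a material cetuximab risk. Section 2.3.1.2 says it can appear days to months after treatment starts, and both that section and Table 15 name abnormal electrolytes as a possible predisposing factor for cardiopulmonary arrest or sudden death. Table 15 tells the reader how that risk is controlled. Sites, however, work from the Schedule of Activities and Appendix 10.2, and these do not require the post-treatment testing that the cardiovascular row describes.

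At stake is whether a stated safety measure is actually carried out. A site can follow the schedule exactly and not deliver the mitigation in Table 15, and a disturbance arising after the last dose could then be picked up later than a reader of the risk table would expect.

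**Working it through.** This is a calendar count; no power or error-rate figure is involved.

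**Inputs**
- Stated monitoring period: 8 weeks after last cetuximab (Table 15), so 8 × 7 = 56 days.
- Stated frequency: weekly (Table 15), so 56 / 7 = 8 tests.
- End-of-treatment visit: 30 ± 7 days after the last study drug, or at the start of further therapy (Section 1.3).
- Follow-Up Visit 1: 3 months ± 7 days after the last study drug (Section 1.3).

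**Fixed tests within days 1 to 56, cetuximab being the last drug given**
1. End of treatment: 30 − 7 = day 23 to 30 + 7 = day 37. Inside the window: 1 test. If further therapy brings the visit forward, it is still one test.
2. Follow-Up Visit 1, with an average month of 30.44 days: 3 × 30.44 = 91.3, so about day 84 to day 98. Outside the window.
3. Sensitivity to month length: with 28-day months, 84 − 7 = day 77; with 31-day months, 93 − 7 = day 86. The earliest possible day is 77, which is after day 56 in every case.
4. Total: 1 fixed test against about 8.

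**Gap between the two fixed visits:** from 84 − 37 = 47 days to 98 − 23 = 75 days with no mandatory electrolyte test.

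**Could another row close the gap?** After treatment, the blood chemistry row in Section 1.3 is marked only at the same two visits, so it adds no time point.

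**Does the count depend on when treatment is taken to end?** The count above ends the on-treatment period at the last dose. If it is instead run to the end of a 21-day cycle, at most 21 / 7 = 3 further weekly tests fall in the window, giving 3 + 1 = 4. That is still half of 8.

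**Exclusion threshold, side by side.** E 01 and the hypomagnesaemia row both exclude values that are low or high. The cardiovascular row names low values only. A high value is therefore excluded by two of the three texts and not mentioned in the third.

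**The case against.** The strongest reply is that the operative sections agree with each other. Section 1.3 and Appendix 10.2 give the same time points, and Appendix 10.2 expressly leaves testing after the last dose to local care. This looks like a deliberate choice, with one summary row left unaligned. Section 2.3.1.2 is also worded as a recommendation, and its grammar ties the weekly frequency to the treatment period, so it is ambiguous about frequency afterwards. The hypomagnesaemia row of Table 15 defers to the protocol and is satisfied by the schedule. All of this is fair, and it narrows the point to the cardiovascular row, supported on duration by Section 2.3.1.2. It does not remove the contradiction, because that row is not worded as optional.

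The count is also conditional. If cetuximab stops and SAR444245 continues, which Section 6.5.1 and Table 7 allow, weekly testing under treatment goes on and more tests fall within the 56 days.

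Three stronger readings are tempting, and the documents do not support them.
- *That post-treatment disturbances would be missed and under-reported.* The schedule keeps tests at two later visits and whenever clinically indicated, and local care may add more. Later detection is the most that can be said.
- *That the 55% incidence of hypomagnesaemia in Section 2.3.1.2 measures the gap.* That is an overall incidence with cetuximab. The protocol gives no rate for events arising after the last dose, and events on treatment fall under the mandatory weekly tests.
- *That two exclusion rules admit different participants.* Eligibility is set by Section 5.2. Anyone below the lower limit is already outside the normal range, so E 01 covers the cardiovascular row in full. Nobody is enrolled under Table 15.

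**Conclusion.** The contradiction on monitoring holds and is in the current text. Table 15's cardiovascular row describes about 8 weekly tests in the 56 days after the last cetuximab dose; the schedule fixes 1. This assumes that cetuximab is the last study drug given and that on-treatment testing ends with the last dose. Relaxing the second assumption raises the count to at most 4. The figure counts fixed tests only, not those prompted by clinical indication or local practice.

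The exclusion threshold is a wording point: Table 15 disagrees with itself, and its cardiovascular row is the outlier against E 01.

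The matter bears on patient safety and on the accuracy of the risk statement, not on the response-rate analysis. It should be corrected, but it is no obstacle to the trial's design.

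**What to change.** Reconcile Section 1.3 and Appendix 10.2 with Table 15 (cardiovascular row) and Section 2.3.1.2, so that the post-treatment electrolyte monitoring that is stated and the monitoring that is scheduled are the same in frequency and duration. The sponsor decides which text stands. If the schedule stands, Table 15 must not claim weekly monitoring for 8 weeks. If Table 15 stands, the schedule and Appendix 10.2 must carry it as a requirement. In either case, say whether the period runs from the last cetuximab dose or from the last dose of any study drug, since Table 15 uses the first and the visit schedule the second.

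In the same edit, reconcile the two exclusion wordings in Table 15 with each other and with E 01 in Section 5.2.

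The cost is a text alignment. If the table's statement is kept, it adds up to 8 − 1 = 7 blood tests per Cohort D2 participant after treatment; if the schedule is kept, the risk table carries a less favourable statement.
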